These data support the rationale for this open-label Phase 2 study, with the aim to evaluate the safety and explore the efficacy of multiple escalating doses of BAY 1093884 in 3 cohorts.

The Phase I study utilized weight-based dosing. The proposed study will use fixed doses. Like most monoclonal antibodies, BAY 1093889 is expected to distribute predominately to the blood plasma and extracellular fluids due to its large molecular weight (18). Preliminary estimations of the volume of distribution at steady-state (V_{ss} , calculated as $[\text{dose}/\text{AUC}] \cdot \text{MRT}$ after IV administration) are in the range of 0.05 to 0.08 L/kg, corresponding to absolute volumes of approximately 3.5 to 5.6 L for a 70 kg individual, and support this expectation. Although blood volume is increased in obese and decreased in underweight individuals when compared to normal weight individuals, these changes are less than proportional with the change in body weight (18). As a consequence, body composition and the presence of excess body weight are of less importance for an antibody when compared to small molecules. Physiologically-based pharmacokinetic (PBPK) modelling was used to predict the variability of PK parameters (AUC , C_{\max} and C_{\min}) and free TFPI levels following a body-weight normalized dose (1 mg/kg) and a flat dose (70 mg) in a population of virtual male individuals with an age range between 18 and 45 years and a weight range between 50 and 110 kg. The flat dosing resulted in slightly lower inter-individual variabilities in BAY 1093884 PK parameters and free TFPI concentrations. Based on general physiological considerations of the distribution properties of antibodies and predictions of the BAY 1093884 PBPK model, it is justified to administer BAY 1093884 in a fixed dose regimen in this dose escalation study.

Data from the Phase 1 study has been used to build a PK/PD model to allow for initial selection of the starting dose (dose X) and it will be further refined with available data generated from the multiple dose levels in this study to select the doses for the subsequent dose levels. The model will be used to project doses that will result in certain duration of

TFPI inhibition and improvement in parameters measured with the thrombin generation assay (TGA) following weekly SC administration. For this projection, to safely evaluate the potential accumulation following multiple administration of BAY 1093884, the lower dose X will provide preliminary safety information, while is not expected to result in meaningful control of bleeding episodes over 7 days. The following Y dose is expected to provide both safety and efficacy data over the 7 days after BAY 1093884 administration. The last dose, Z, is supposed to provide additional efficacy information and safety margin, without exceeding the highest evaluated dose in the Phase 1 study.

The reason to start with 100 mg dose is that this dose is expected to result in 3-5 days of TFPI inhibition. In addition, all subjects have been exposed to 100 mg or more in the Phase 1 study, where the safety of this dose has been established. In fact, single doses of 1 mg/kg (68 - 91 mg), 3 mg/kg (213 - 270 mg) and 6 mg/kg (401 - 510 mg) have been administered in the Phase 1 study.

The rationale to include in the study both subjects treated on demand and subjects on prophylaxis who present at least 4 bleeding episodes in the previous 6 months is to ensure enrollment of subjects with high unmet need (at least 8 bleeds per year). It is well known that the annualized bleeding rate in subjects on prophylaxis is between 1 and 3 for non-inhibitor subjects (19, 20) and approximately 5 for inhibitor subjects (21).

Subjects treated on demand with previously assigned products will switch to prophylaxis with BAY 1093884, which is expected to lead to similar or lower bleeding rates. Subjects previously treated prophylactically may benefit from the study drug because of their high bleeding rate (despite frequent regular injections). In any case, any occurring bleed that will need additional control will be treated with their pre-study treatment (with already proven response) and subjects will be always allowed to continue the study or to interrupt it, based on their response to treatment and treatment satisfaction.

End of study

The end of the study as a whole will be reached as soon as the last visit of the last subject has been reached in all centers in all participating countries (EU and non-EU).

Primary completion

The primary completion event for this study is when the last subject in Cohort 3 has completed 24 weeks of treatment (end of Part B).

Communication plan

A communication plan is in place to outline how the safety data and dose escalation decision will be communicated to all investigator sites.

Routine updates via email, newsletter, or teleconference will be provided to the investigators throughout the course of the study to facilitate communication of new safety data from treated patients from the ongoing studies. DMC recommendations, including dose escalation decision, will be communicated to the investigators in a timely manner.

6. Study population

6.1 Inclusion criteria

1. Male severe hemophilic patients with undetectable FVIII activity <1% or FIX activity <2%, with or without inhibitors (any titer) are eligible.

Note: Subjects with a past history of inhibitors (any inhibitor titer) are eligible.

2. Age ≥ 18 years.
3. Documentation of ≥ 4 bleeding episodes (any type or location of bleeds, treated or not) within the 6 months prior to screening.
4. For subjects on prophylaxis: Willingness to interrupt ongoing prophylaxis.
5. For subjects on ITI: willingness to interrupt ongoing ITI
6. Signed informed consent.

6.2 Exclusion criteria

1. History of any other coagulation disorder (particularly disseminated intravascular coagulopathy or combined FVIII/FV deficiency) or platelet disorder.
2. History of diseases related to venous thromboembolic events (e.g., pulmonary embolism, deep vein thrombosis, thrombophlebitis) or thrombotic microangiopathy.
3. Risk factors for venous or arterial diseases (e.g., uncontrolled hypertension, uncontrolled diabetes).
4. History of cardiac, coronary and/or arterial peripheral atherosclerotic disease, particularly myocardial infarction, cerebrovascular accident, stroke, transient ischemic attack, congestive heart failure, angina pectoris or treatment for angina pectoris.
5. Platelet count <100,000/ μL .
6. Human immunodeficiency virus (HIV) infection with a cluster of differentiation 4 (CD4+) lymphocyte count of <200/ mm^3 .
7. Any planned major surgical intervention.
8. Subjects with known or suspected hypersensitivity to trial product(s) or related products.
9. Subjects with known autoimmune disease or on treatment with immune-modulatory drugs.
10. Subjects with advanced liver disease (Child-Pugh Grade B and C) or with signs of liver function impairment (e.g., alanine aminotransferase [ALT] and aspartate aminotransferase [AST] levels $>3 \times$ the upper limit of the normal range and/or total bilirubin $>2 \times$ the upper limit of the normal range).
11. Subjects with serum creatinine $>2.0 \times$ the upper limit of the normal range.
12. Treatment with an investigational drug within 3 months prior to screening visit.
13. Subjects not willing to stop prophylaxis or ITI.

6.3 Withdrawal of subjects from study

6.3.1 Withdrawal

Withdrawal criteria

Subjects *must* be withdrawn from the study if any of the following occurs:

- At their own request or at the request of their legally acceptable representative. At any time during the study and even without giving reasons, a subject may decline to participate further. The subject will not suffer any disadvantage as a result.
- Development of an inhibitory antibody to BAY 1093884 that neutralizes the activity sufficiently to interfere with effective treatment.
- Failure to comply with scheduled appointments for study-related testing or with Electronic Patient Diary (EPD) data entry to an extent that compromises collection of critical data
- Significant concurrent illness or deterioration in the subject's condition, including laboratory values that the investigator deems to be incompatible with the subject's continued safe participation in the study.

In all cases, the reason for withdrawal must be recorded in the case report form (CRF) and in the subject's medical records

At the time of discontinuation, the subject should be scheduled to perform the procedures and evaluations required at the final study visit.

Subjects *may* be withdrawn from the study if any of the following occurs:

- Violation of eligibility criteria;
- Withdrawal of a subject at the specific request of the Sponsor;
- Withdrawal of a subject at the Investigator's request. As examples: If the Investigator considers that the subject's health is compromised by remaining in the study or if a subject on the highest dose (without possibility for dose escalation) presents excessive uncontrolled bleeding; or the subject is not sufficiently cooperative;
- Withdrawal of a subject from the study if the subject is lost to follow-up.

Depending on the time point of withdrawal, a withdrawn subject is referred to as either "screening failure" or "dropout" as specified below:

Screening failure

A subject who, for any reason (e.g., failure to satisfy the selection criteria), terminates the study before the time point used for the definition of "dropout" (see below) is regarded a "screening failure."

Re-starting the defined set of screening procedures to enable the "screening failure" subject's participation at a later time point is not allowed – with the following exceptions:

- The subject had successfully passed the screening procedures, but could not start subsequent treatment on schedule.
- Initial screening occurred too early to complete the required washout period after prior therapy.
- The in-/exclusion criteria preventing the subject's initial attempt to participate have been changed (via protocol amendment).

Thus, participation of an initial "screening failure" subject at a later time point even if he meets all selection criteria upon re-screening is not acceptable.

In any case, the investigator has to ensure that the repeated screening procedures do not expose the subject to an unjustifiable health risk. In addition, the subject must re-sign the informed consent form during re-screening, even if it was not changed after the subject's previous screening. If a subject is re-screened, he will be assigned a new subject number.

Dropout

A subject who discontinues study participation prematurely for any reason is defined as a "dropout", if the subject has received at least 1 dose of BAY 1093884.

General procedures

In all cases, the reason for withdrawal must be recorded in the electronic case report form (eCRF) and in the subject's medical records.

The subject may object to the generation and processing of post-withdrawal data as specified in Section 13.4.

Completer

A subject is defined as completer if he has completed at least Part A, a minimum of one Part B, and has performed a final visit.

6.3.2 Replacement

If fewer than 6 subjects per cohort will complete 6 weeks, additional subjects will be recruited to achieve the target sample size of 6 subjects for DMC review. Subjects may be replaced only if they have not withdrawn from the study for drug-related safety concerns.

If inhibitor subjects with less than 24 weeks of treatment or PK subjects with less than 12 weeks of treatment drop out, additional subjects will be recruited to ensure that at least 2 PK subjects (with complete PK evaluations) and at least 1 evaluable inhibitor subject are included in each dose cohort.

6.4 Subject identification

Upon enrollment, each subject will receive a unique subject number. Screening procedures will be performed and eligibility for the study confirmed. Once assigned to a subject the unique subject number must not be used for another subject within this study.

The subject number is a 9-digit number consisting of:

Digits 1 to 5 = Unique center number

Digits 6 to 9 = Current subject number within the center

7. Treatments

During the extension part, subjects will continue treatment with BAY 1093884 either on their current dose or escalate to the next higher opened dose (dose Y for subjects currently on dose X, dose Z for subjects currently on dose Y), after safety and efficacy evaluations every 12 weeks (including DMC evaluation, where appropriate), if dose escalation criteria are met. The extension part will be initiated only after DMC evaluation of safety data from the 6 patients in the dose Z cohort for 6 weeks, and continued pending submission of safety and efficacy data to Health Authorities after 12 months from the start of the extension part, and every 12 months thereafter until Marketing Authorization.

For further details, see Section 5.

7.1.2 Treatment of bleeds

The occurrence of bleeds of different cause, severity and site is a typical characteristic of subjects with hemophilia, being the clinical manifestation of the disease itself.

Bleeds will be classified into the following types:

- **Spontaneous:** Not attributable to any trauma or activity
- **Non-spontaneous/non-traumatic:** Not related to a trauma, but due to activity (walk, run, sport, gym, etc.)
- **Traumatic:** Related to an identified trauma

Throughout the study, all bleeds will be recorded, but only the bleeds recorded as “spontaneous” (not related to any trauma or activity) and “requiring additional treatment” will constitute the base for the efficacy evaluation.

All bleeds occurring in subjects receiving prophylactic treatment with BAY 1093884 after Visit 2 (“Start of treatment with BAY 1093884”) which require additional treatment will be treated according to the subject’s pre-study treatment as outlined in Section 8.1. Given the potential additive effect of BAY 1093884 and concomitant medication, it is recommended to treat the bleeds with the lowest approved doses of the prescribed replacement factor or bypassing agent, and repeat the dose, if additional doses will be needed, at the investigator’s judgment.

For the same reason, the investigator must carefully consider the intensity and the location of a trauma for which bleeding has not yet occurred before the preventive use of a replacement factor or a bypassing agent during treatment with BAY 1093884. Careful oversight of bleed treatment by the Investigators will ensure the patients’ safety.

If a bleed occurs on a day of the planned injection of BAY 1093884, the subject should treat the bleed with his usual medication and administer the scheduled prophylactic injection of BAY 1093884. The injection schedule with BAY 1093884 will not be affected by the treatment of bleeds.

7.1.3 Treatment for PK/PD assessments

PK assessment using dense sampling will be done in a subset of 2 subjects (PK subjects) after the first administration and after the last administration of BAY 1093884 during Part A of each dose cohort (X mg, Y mg, or Z mg). Sparse PK samples will also be collected from the all other subjects in the study.

The wash-out times for FVIII, FIX products and FEIBA as listed in Section 7.1, Table 7-2, must be observed prior the first injection of BAY 1093884.

For PK subjects: Blood samples will be drawn pre-dose and 4 h (Visits 2.1 and 6.1, respectively), 24 h (Day 1; Visits 2.2 and 6.2, respectively), 96 h (Day 4; Visits 2.3 and 6.3, respectively) and 168 h (Day 7; Visits 3.1 and 6.4, respectively) post-dose after the first and the last dose in the first 12-week period. Further PK samples will be collected during the visits at Weeks 3 and 6. After the first 12-week period, at each planned visit in the hospital, one sparse PK sample will be drawn in all subjects (including non-PK subjects) regardless of the wash-out time for bypassing agents or replacement factors (if taken for the treatment of bleed). At all these visits, subjects should come to the site prior to the scheduled BAY 1093884 injection.

For non-PK subjects: The wash-out times for FVIII, FIX products and FEIBA as listed in Section 7.1, Table 7-2, must be observed prior the first injection of BAY 1093884.

Following the collection of the baseline sample, one sparse PK sample will be drawn at each planned site visit regardless of the wash-out of bypassing or replacement agents (if taken for treatment of bleed). Sparse PK samples will also be drawn regardless of study drug intake, except for Visit 6, Visit 7 and the Every 12-week Visit, when the subject should come to the site prior to the scheduled BAY 1093884 injection.

PD assessments will be done in all subjects as outlined in Section 9.

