9.2 Visit description

9.2.1 Visit description for non-PK subjects

The following flow chart and visit descriptions apply to non-PK subjects. The corresponding visit descriptions for PK subjects are provided in Section 9.2.2.

Note: For many visits, the same general assessments apply for PK subjects compared with non-PK subjects, however, PK subjects must always come to site on the day of the scheduled

injection, without having injected yet for the first 12 weeks. While for non-PK subjects this only applies at Visits 2 and 6. Therefore, the visit windows are often more stringent for PK subjects (see [Table 9-4](#), and [Table 9-5](#) for details). From “Part B” onwards, visits for PK and non-PK subjects are the same.

Integrated Clinical Study Protocol
BAY 1093884 / 19580

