05 APR 2019

Version 4.0

Page: 39 of 96

Table 9–2 Tabular schedule of assessments (subjects not participating in PK evaluations; Screening and Part A)

Non-PK subjects	Screening		Part A					
	Visit 1		Visit 2	Visit 3	Visit 4	Visit 5	Phone call Week 9	Visit 6
Visit Name	Screening	Eligibility check	Start of treatment	Week 1	Week 3	Week 6		Week 12
Time	≤6 wks before V2	2-3 wks before V2	≤6 wks after V1	1 wk ± 1 d after V2	3 wks ± 2 d after V2	6 wks ± 2 d after V2	3 wks ± 2 d after V5	12 wks ± 1 d after V2
Procedures								
Informed consent	X							
Eligibility check	X	X ^a	X ^a					
Demographic data	X							
Med., disease and surgical history	X							
Medication history	X							
Physical examination	X		X ^m	X	X	X		X ^m
Vital signs	X		X ^b	X	X	X		X ^b
Blood sampling	X ^{f,g,h}		X ^{g,i,j,k,m}	X ^{g,i,j}	X ^{g,i,j}	X ^{g,i,j}		X ^{g,i,j,m}
Adverse events	X		X	X	X	X	X	X
Concomitant medication	X		X	X	X	X	X	X
EPD device: training and dispense	X							
EPD device: review			X	X	X	X	X	X
EPD device: return								
Remind subject on wash-out from pre-study product before next visit	X							
Subject to come to site taking wash-out from pre-study product into account	X		X					
Body weight	X		X					X
Local 12-lead ECG			X	X	X	X		X
Confirm eligibility in IWRS to trigger first shipment of study drug		X						
HJHS			X					
Administration of study drug			X					X ^c
Dispense study drug for home infusions			X					X
Return used and unused vials of study drug								X
Plan next visit on day of scheduled injection with BAY 1093884. Reminder to subjects to come next visit un-injected							X	X ^d
Subject to come un-injected								X
Evaluate dose escalation criteria								X
Start 4-weekly contact with subjects								X ^d
Schedule additional safety visits 1 week ± 1 day and 6 weeks ± 1 day after dose escalation								X ^e

Abbreviations: d = day, ECG = Electrocardiogram, EPD = Electronic patient diary, HJHS = Hemophilia Joint Health Score, IWRS = Interactive web responding system, PK = Pharmacokinetic, V = visit, wk = week

Integrated Clinical Study Protocol
BAY 1093884 / 19580

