05 APR 2019

Version 4.0

Page: 40 of 96

Table 9–3 Tabular schedule of assessments (subjects not participating in PK evaluations; Part B through end of study)

Non-PK subjects	Start of Part B to End of Study	Study Part Independent Visits		
		Additional safety visits if dose escalated	Final visit or Early termination visit	Follow-up phone call
Visit Number	Visit 7 and every 12 weeks after Visit 7			
Visit Name	Week 24 onward			
Time	24 wks ± 7 d after V2 ⁿ Every 12 wks ± 7 d after V2 ⁿ	1 wk ± 1 d after previous visit and 6 wks ± 1 d		4 wks ± 2 d after Final/Early Termination visit
Procedures				
Physical examination	X ^m	X	X	
Vital signs	X ^b	X	X	
Local 12-lead ECG	X	X		
Body weight	X			
Blood sampling	X ^{g,i,j,m}	X ^{g,i,j}	X ^{g,i,j}	
Adverse events	X	X	X	X
Concomitant medication	X	X	X	X
EPD device: training and dispense				
EPD device: review	X	X	X	
EPD device: return			X	
HJHS			X	
Administration of study drug	X ^c			
Dispense study drug for home infusions	X			
Return used and unused vials of study drug	X		X	
Plan next visit on day of scheduled injection with BAY 1093884. Reminder to subjects to come next visit un-injected	X ^d	X		
Subject to come un-injected	X			
Evaluate dose escalation criteria	X			
Start 4-weekly contact with subjects	X ^d	X		
Schedule additional safety visits 1 week ± 1 day and 6 weeks ± 1 day after dose escalation	X ^e			

- a Confirmation of eligibility including check of laboratory test results
- b To be performed before and 30-60 minutes after study drug administration
- c If the subject meets the dose-escalation criteria, the subject will receive the next higher dose; to be done under medical supervision
- d If subject maintains current dose
- e If subject is escalated to higher dose
- f Only in subjects who consented to the optional pharmacogenetic research project: Blood sampling for pharmacogenetics (PgX). Once consent is obtained, the sample may be taken at any time point during the study.
- g Blood sampling for CBC, platelets, serum chemistry
- h Blood sampling for FVIII/FIX level and FVIII/FIX inhibitor level
- i Blood sampling for aTFPI-Ab
- j Blood sampling for PK, PD and exploratory biomarkers
- k Blood sampling for low-density lipoprotein (LDL)
- m To be performed prior to study drug administration
- n Visit windows of ±7 days (calculated from Visit 2) are allowed, but the next scheduled BAY 1093884 injection must be kept in mind to ensure subjects will not have >8 days in between 2 injections of BAY 1093884.

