4.1 General Principles

The statistical evaluation will be performed by using the software package SAS release 9.2 or higher (SAS Institute Inc., Cary, NC, USA).

All data (efficacy, safety, PK/ PD, and demographic data) will be listed and study summary tables will be provided where appropriate. Variables measured on metrical scales will be summarized using descriptive statistics that will include: the number of non-missing observations, the arithmetic mean, the sample standard deviation, the median, the minimum and maximum, as well as the first and third quartiles where appropriate. Frequency tables will be provided for variables measured on ordinal or nominal scales. Tables will display the number and percentage of subjects falling within a particular category.

Data will be displayed by dose cohort and by study medication actually received during the respective study parts and their visits.

Data will be displayed by period of time. This includes:

- Part A: The first 12 weeks of treatment of each subject.
- Part B: The additional 12-week periods of treatment after Part A. Each subject will be analyzed in the dose cohort he was assigned to (data of dose escalated subjects will be not included).

In general, data will be displayed as measured at each scheduled time point, individual values will be presented in listings.

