6.3 Pharmacokinetics/pharmacodynamics

All PK analyses will be based on the PK set.

Descriptive statistics for PK data will be presented as n, geometric mean, geometric standard deviation, geometric coefficient of variation, arithmetic mean, standard deviation (SD), median, minimum, and maximum.

The changes in PK parameters across the dose range studied may be assessed by comparisons of the above variables at each dose level. BAY 1093884 plasma concentrations will be plotted as a function of time for each subject according to dose.

Plots of summary data for each dose (geometric mean and arithmetic mean plasma concentrations at each time point) will also be presented on both linear and logarithmic scales. BAY 1093884 plasma levels may also be plotted to evaluate the correlation of plasma levels with safety and other endpoints.

PD parameters will be analyzed descriptively and with statistical models as appropriate.

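### PD summaries at Weeks 1, 3 and 6 mix early post-dose and end-of-interval samples, because non-PK subjects are sampled untimed there and the SAP has no time-since-injection rule

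*Protocol*

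**What the plan says.** Protocol 7.1.3, on non-PK subjects: "Sparse PK samples will also be drawn regardless of study drug intake, except for Visit 6, Visit 7 and the Every 12-week Visit". Protocol 9.2.1 says that PK subjects must attend un-injected throughout the first 12 weeks, and adds: "While for non-PK subjects this only applies at Visits 2 and 6". Table 9-2 agrees, marking un-injected attendance only at Week 12. The procedures for Visit 3, reused for Visits 4 and 5 (Protocol 9.2.1.4 to 9.2.1.6), contain no pre-injection step. The matching PK-subject visits (9.2.2.6 to 9.2.2.8) all do.

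PD is part of the same bleed. Footnote j to the schedule tables reads "Blood sampling for PK, PD and exploratory biomarkers" and is attached to Visits 3, 4 and 5. The windows in Table 9-2 are "1 wk ± 1 d after V2" for Visit 3 and "3 wks ± 2 d after V2" for Visit 4; Visit 5 also has 2 days either side. Injections are 7 days apart, give or take 1 day (Table 7-1).

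On analysis, SAP 4.1 says: "In general, data will be displayed as measured at each scheduled time point". SAP 6.3 says: "PD parameters will be analyzed descriptively and with statistical models as appropriate". Neither mentions time since injection. Protocol 9.5.1.1 promises actual sampling times for PK parameters but makes no such statement for PD.

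**The concern.** The PD target that Protocol 7.4.1.1 sets for doses Y and Z is an effect lasting at least the whole 7-day interval. Only a sample near the end of the interval tests that. A sample taken a day or two after an injection says little about it.

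At Weeks 1, 3 and 6 a by-dose PD summary would combine about 2 subjects known to be at the end of the interval with about 6 whose timing is unspecified. For a dose whose effect fades within the week, the summary can show activity that is absent at day 7. That blurs the contrast with a dose whose effect lasts.

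Timing also matters for safety. Protocol 10.5 compares dose levels on thrombosis and hemostasis markers when clinical and laboratory safety are comparable, and a marker level of unknown timing is hard to compare between doses.

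Up to Week 6, the minimum follow-up for opening the next cohort, non-PK subjects have no post-baseline visit that must be pre-dose. Their first is Week 12.

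**Working it through.** The plan states no figure on this point, so there is none to reproduce. What follows is an illustration.

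**Inputs**
- 8 subjects per cohort (Protocol 5), with 2 densely sampled (Protocol 7.1.3): 8 - 2 = 6 non-PK.
- Visit windows: Week 1 is day 6 to 8, Week 3 is day 19 to 23, Week 6 is day 40 to 44 (Table 9-2).
- Injection interval: 6 to 8 days (Table 7-1).
- Duration of effect at dose X (Protocol 5, justification of design): "The reason to start with 100 mg dose is that this dose is expected to result in 3-5 days of TFPI inhibition".

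**Possible times since the last injection, non-PK subjects**
- Injections exactly every 7 days. At Week 1 the second injection is on day 7 and the visit on day 6 to 8, so the sample falls 0-1 or 6-7 days after an injection. At Weeks 3 and 6 the window is 2 days either side of an injection day, giving 0-2 or 5-7 days.
- Injections drifting within 6 to 8 days. At Week 1 the second injection is itself on day 6 to 8, giving 0-2 or 6-8 days and still nothing in mid-interval. By Week 3 the dosing day can have moved 3 x 1 = 3 days either way, and by Week 6 up to 6 x 1 = 6 days, so anything from 0 to 8 days is possible.

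**Share reading as active**

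Assume that the effect is fully on from injection until day 3 (or day 5) and then off, and that visits are uniform within their windows. Let p be the share of non-PK samples inside the effect. The expected number active is 6p, and the share of the cohort is 6p/8, because the 2 PK subjects are pre-dose and count as inactive.

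With exact weekly dosing, half the visits fall after the injection (0-2 days, inside either duration) and half before it (5-7 days or later, outside both). So p = 0.50, 6 x 0.50 = 3.0, and 3.0/8 = 37.5%.

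With intervals uniform on 6 to 8 days and drift accumulating (simulation, 400,000 draws):

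| Visit | p, 3-day effect | Active of 8 | p, 5-day effect | Active of 8 |
|---|---|---|---|---|
| Week 1 | 0.50 | 3.0 (37.5%) | 0.50 | 3.0 (37.5%) |
| Week 3 | 0.48 | 2.9 (36%) | 0.58 | 3.5 (44%) |
| Week 6 | 0.46 | 2.7 (34%) | 0.63 | 3.8 (47%) |

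Counts use unrounded p. The range is therefore 2.7 to 3.8 of 8, or 34-47%. On the same assumptions about 0 of 8 would be active at day 7.

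The chance that at least 4 of the 6 non-PK subjects read as active is the binomial tail. For p = 0.50 it is (15 + 6 + 1)/64 = 0.34. Across the table it runs from 0.27 (Week 6, 3-day effect) to 0.60 (Week 6, 5-day effect).

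**The case against.** The strongest reply is that no identified decision rests on these summaries. Doses Y and Z are proposed from an updated PK/PD model (Protocol 7.4.1.1), and a model using actual times is not harmed by varied sampling times; it may even gain from them. Week 12, Week 24 and later 12-weekly samples are pre-dose for everyone. The PK subjects have samples at 4, 24, 96 and 168 hours after the first and last Part A doses. Individual values are listed, and the additional SAP plans individual PK/PD plots. The display rule is only a general principle, and SAP 6.3 specifies no by-visit PD table. All of this stands. It confines the problem to descriptive PD summaries at Weeks 1, 3 and 6, but does not remove it, because the SAP states no other display rule.

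Some stronger readings are tempting and are not supported:
- A reader might infer that a dose that wears off could be taken forward as active. The model, the later pre-dose samples and the dense profiles all stand against that. In Protocol 10.5 efficacy is judged on bleeds, and the markers serve the safety comparison.
- A reader might spread the samples evenly over the week, giving 6 x (3/7)/8 = 32% to 6 x (5/7)/8 = 54%. The visit windows contradict even spread: mid-interval sampling cannot occur at Week 1, and at Weeks 3 and 6 it needs the dosing day to drift.
- A reader might call the early samples near-peak. The documents give no time to peak, and a sample taken minutes after a subcutaneous injection may look much like a pre-dose one.
- A reader might count the post-escalation safety visits as untimed too. There the documents conflict: one sentence of Protocol 7.1.3 has all subjects attend before injection at planned visits after 12 weeks, while its non-PK exception list omits the safety visits and Tables 9-3 and 9-5 carry no un-injected mark for them.

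**Conclusion.** The point holds for Weeks 1, 3 and 6. If the SAP is followed as written, descriptive PD summaries at those visits mix early post-dose and end-of-interval values, and mix untimed non-PK with pre-dose PK subjects.

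The 34-47% is an order of magnitude for dose X only. It rests on an on/off effect with immediate onset, visits uniform within their windows and no effect left at day 7. Protocol 7.4.1.1 describes dose X as giving at least 3 to 5 days, and the protocol anticipates possible accumulation, so the true day-7 count could exceed 0. A delayed onset would lower the early readings. Doses Y and Z are meant to act for at least 7 days, so the illustration does not carry over to them. The defect is one of description and interpretation, and it is cheap to correct.

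**What to change.** In SAP 6.3, derive for each PD sample the actual time since the last BAY 1093884 injection, from the diary or CRF injection time and the actual draw time. Then:
- Summarise Week 1, 3 and 6 PD by time-since-injection category within dose.
- Base statements about 7-day PD duration only on end-of-interval, pre-dose samples.
- Give early post-dose samples their own by-dose summary. With trough-only tables, an early rise in a thrombosis marker could be missed.

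Injection times are already recorded (Protocol 7.7 and 9.4.1), and Protocol 9.5.1.1 requires actual sampling times on the eCRF. The cost is SAP wording, one derived variable, and fewer subjects per category at those weeks. The sampling procedure at Visits 3 to 5 need not change.

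Separately, reconcile the two statements in Protocol 7.1.3 with each other and with Tables 9-3 and 9-5 on whether subjects attend the post-escalation safety visits before injection.
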